## Appendix 3 Clinical Laboratory Tests

### Enzyme-linked immunosorbent assay

Anti-gE ELISA is a two-step ELISA based on the antibody and antigen interaction, which allows the detection and the quantification of specific immunoglobulin G (IgG) antibodies directed against gE in tested serum samples.

Briefly, diluted serum samples are added onto a 96-polystyrene-well microplate pre-coated with gE. Then goat antibodies directed against human IgG antibodies and conjugated to horseradish peroxidase (a-IgG-HRP) are added and will bind to anti-gE IgG if present. After a washing step, the addition of a chromogen-substrate solution specific for HRP will provide means of detecting the anti-gE specific for the pre-coated antigen. The HRP catalyzes an enzymatic reaction which is stopped by the addition of sulphuric acid, resulting in a color change from blue to yellow.

The optical density recorded is proportional to the concentration of the anti-gE antibodies present in the serum sample. Antibody titre is expressed in mIU/mL.

## Appendix 4      Adverse Events: Definitions and Procedures for Recording, Evaluating, Follow-up, and Reporting

### Adverse Events

AE Definition

An AE is any untoward medical occurrence in a patient or clinical study participant that is temporally associated with the use of study intervention, whether or not considered related to the study intervention.

 
An AE can, therefore, be any unfavorable and unintended sign, symptom, or disease (new or exacerbated) temporally associated with the use of study intervention.

Events Meeting the AE Definition

Significant or unexpected worsening or exacerbation of the condition/indication under study.

Exacerbation of a chronic or intermittent pre-existing condition including either an increase in frequency and/or intensity of the condition.

New conditions detected or diagnosed after study intervention administration even though they may have been present prior to the start of the study.

Signs, symptoms, or the clinical sequelae of a suspected interaction.

Signs, symptoms, or the clinical sequelae of a suspected overdose of either study intervention.

Signs or symptoms temporally associated with study intervention administration.

Signs, symptoms that require medical attention (e.g., hospital stays, physician visits, and emergency department visits).

Pre- or post-intervention events that occur as a result of protocol-mandated procedures (i.e., invasive procedures).

Clinically significant abnormal laboratory findings following the start of the study.

Events NOT Meeting the AE Definition


Situations where an untoward medical occurrence did not occur (e.g., social and/or convenience admission to a hospital, admission for routine examination).

Anticipated day-to-day fluctuations of pre-existing disease(s) or condition(s) present or detected at the start of the study that do not worsen.

Pre-existing conditions or signs and/or symptoms present in a participant prior to the first/the study vaccination. These events will be recorded in the medical history section of the eCRF.

Hospitalization for elective treatment of a pre-existing condition (known or diagnosed prior to informed consent signature) that did not worsen from baseline.

Clinically significant abnormal laboratory findings or other abnormal assessments, unless judged by the investigator as more severe than expected for the participant's condition, or that are present or detected at the start of the study and do not worsen.

However, if 1 or both of the following conditions apply, then the event should be reported promptly to IQVIA as an SAE:

The event is, in the investigator's opinion, of greater intensity, frequency, or duration than expected for the individual participant, or

The investigator considers that there is a reasonable possibility that the event was related to the administration of the study intervention.

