**Table 9** **Study Holding Rules**

Holding Rule	Event	Number of participants to pause vaccination in all groups, pending further evaluation by IDMC
1	Any death considered at least possibly related to study vaccination	≥ 1
2	Any SAE(s) considered at least possibly related to vaccination	≥ 1
3	Same or similar* Grade 3 unsolicited AE considered to be at least possibly related to vaccination	≥ 2

[figure not shown]
AE = adverse event; IDMC = Independent Data Monitoring Committee; SAE = serious adverse event

\*based on medical judgment

If the investigator becomes aware of a holding rule being met, he/she must suspend administration of the study intervention, pause enrollment, and inform IQVIA immediately (e.g., holding rules 1-3). Refer to [Appendix 4](#) for contact information.

GSK via IQVIA will inform all study investigators to suspend the study intervention and enrollment if any of the holding rules are met.

The following communication sequence for the identification of holding rules by the investigator must be followed ([Figure 2](#)).

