## Serious Adverse Events

If an event is not an AE per definition above, then it cannot be an SAE even if serious conditions are met (e.g., hospitalization for signs/symptoms of the disease under study).

An SAE is defined as any untoward medical occurrence that, at any dose:
a) Results in death
b) Is life-threatening
The term “life-threatening” in the definition of “serious” refers to an event in which the participant was at risk of death at the time of the event. It does not refer to an event that hypothetically might have caused death had it been more severe.
c) Requires inpatient hospitalization or prolongation of existing hospitalization
In general, hospitalization signifies that the participant has been admitted at the hospital or emergency ward for observation and/or treatment that would not have been appropriate in the physician’s office or in an out-patient setting. Complications that occur during hospitalization are also considered as AEs. If a complication prolongs hospitalization or fulfills any other serious criteria, the event will also be considered serious. When in doubt as to whether “hospitalization” occurred or was necessary, the AE should be considered serious.
d) Results in disability/incapacity
The term disability means a substantial disruption of a person’s ability to conduct normal life functions. This definition is not intended to include experiences of relatively minor medical significance such as uncomplicated headache, nausea, vomiting, diarrhea, influenza-like illness, and accidental trauma (e.g., sprained ankle) which may interfere or prevent everyday life functions but do not constitute a substantial disruption.
e) Other situations

 
Medical or scientific judgment should be exercised in deciding whether reporting is appropriate in other situations, such as important medical events that may not be immediately life-threatening or result in death or hospitalization but may jeopardize the participant or may require medical or surgical intervention to prevent one of the other outcomes listed in the above definition. These should also be considered serious. Examples of such events are invasive or malignant cancers, intensive treatment in an emergency department or at home for allergic bronchospasm, blood dyscrasias, or convulsions that do not result in hospitalization.
 

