18.1.4. SERIOUS AEs

For each study group, the incidence rates (frequencies and percentages) of participants with SAE occurring post-dose of study interventions at Day 1 will be presented by SOC and PT. Similar tabulation will be done for SAE with causal relationship to vaccination as assessed by the investigator; for fatal SAE and for causally related fatal SAE. Serious AEs will be recorded on the "Expedited Adverse Events" page of the eCRF. The incidence rates of participants with serious AEs will be summarized by country.

Listings of AEs and SAEs leading to discontinuation of study will be provided.

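### Appendix 4 tells sites to report certain events as SAEs on grounds that are not seriousness outcomes, which conflicts with the protocol's own SAE definition and can reach the SAE endpoint and holding rule 2

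*Protocol*

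**What the plan says.** Protocol Appendix 4 (Adverse Events) has a box titled "Events NOT Meeting the AE Definition". Its last bullet begins with a reservation and sets two conditions. If one or both apply, "then the event should be reported promptly to IQVIA as an SAE". The conditions are:

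1. The event is, in the investigator's opinion, "of greater intensity, frequency, or duration than expected for the individual participant".
2. "The investigator considers that there is a reasonable possibility that the event was related to the administration of the study intervention".

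The section that follows, on serious adverse events, opens with the opposite rule: "If an event is not an AE per definition above, then it cannot be an SAE even if serious conditions are met". It then defines an SAE by five kinds of outcome, a) to e): death, threat to life, hospitalization, disability, and other medically important situations. Later in the same appendix, the section on intensity says again that an event is serious only through those outcomes, and warns against confusing severity with seriousness.

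The box just before the not-an-AE list counts this as an ordinary AE: "Exacerbation of a chronic or intermittent pre-existing condition including either an increase in frequency and/or intensity of the condition".

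Two parts of the plan depend on the SAE label:

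- **Endpoint.** Protocol Table 5 makes the percentage of participants reporting SAEs a secondary endpoint. SAP 18.1.4 tabulates "the incidence rates (frequencies and percentages) of participants with SAE occurring post-dose of study interventions at Day 1", with a further table for causally related SAEs.
- **Holding rule 2.** Protocol Table 9 names the event as "Any SAE(s) considered at least possibly related to vaccination" with a threshold of one participant. Section 8.2.3.1 limits the rule to the first 200 participants enrolled.

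**The concern.** The two conditions measure how bad an event is relative to expectation and whether the vaccine might have caused it. Neither asks what happened to the child. An instruction that turns either one into an SAE report therefore produces a different set of SAEs from the one defined by outcomes. It does so for events that the same box has just said are not AEs at all.

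Two results are exposed. The SAE percentage could depend on which paragraph of Appendix 4 a site follows, and SAP 18.1.4 describes no check of seriousness before an event is counted. The second condition is also, in substance, the relatedness part of holding rule 2. A non-serious event reported under it would meet that rule on its wording and pause vaccination in all groups until the IDMC has evaluated it. The rule in Table 9 that is written for severity, rule 3, asks for more: at least two participants with the same or a similar related Grade 3 event.

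**Working it through.** **Step 1. The passages side by side.**

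| Place in Protocol Appendix 4 | Event described | Label given | Seriousness outcome needed? |
|---|---|---|---|
| Events meeting the AE definition | Pre-existing condition, more frequent or more intense | AE | No |
| Events not meeting it, last bullet | Worse than expected, or possibly related | SAE | No |
| Serious Adverse Events, opening line | Anything that is not an AE | Cannot be an SAE | Not applicable |
| Serious Adverse Events, a) to e) | Untoward occurrence with a listed outcome | SAE | Yes |
| Assessment of Intensity and Toxicity | Any event called serious | Serious only by outcome | Yes |

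The second row cannot hold together with the third and fourth. If an event stays on the not-an-AE list, the third row forbids the SAE label. If worsening is taken to turn it into an AE, the fourth row still asks for an outcome that the bullet does not require. These passages are all current text, not amendment history.

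**Step 2. The plan's own precision for a rare event.** The nearest figure is in Protocol Table 10: 0 of 200, exact 95% CI 0.00% to 1.83%. For zero events the Clopper-Pearson upper limit is 1 − 0.025^(1/200) = 1.83%, so the figure reproduces.

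**Step 3. Effect on the endpoint.** With 200 children per group (VV lots pooled), one reclassified child adds 1/200 = 0.5 percentage points. Starting from no SAEs, the exact intervals are:

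- 0/200 = 0.0%, 95% CI 0.00% to 1.83%
- 1/200 = 0.5%, 95% CI 0.01% to 2.75%
- 2/200 = 1.0%, 95% CI 0.12% to 3.57%

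**Step 4. Chance of meeting holding rule 2.** Let p be the proportion of children with a non-serious event that is judged possibly related and is reported as an SAE because of the bullet. The documents give no value for p, so every value below is an assumption. With a threshold of one among 200 children, treated as independent, the chance of at least one trigger is 1 − (1 − p)^200.

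| Assumed p | Expected number in 200 (200p) | Chance of at least one |
|---|---|---|
| 0.01% | 0.02 | 2% |
| 0.05% | 0.1 | 9.5% |
| 0.1% | 0.2 | 18% |
| 0.5% | 1.0 | 63% |

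The result is driven entirely by p. The calculation shows only how sensitive a threshold of one is; it does not forecast a pause.

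**The case against.** The strongest reply is that the bullet reaches very little. The entries on pre-existing disease in the not-an-AE list cover conditions that have not worsened, so condition 1 nearly cancels them. A child whose eczema flares more than usual is a tempting example, but that event falls in the preceding box as an ordinary AE and never enters this list. The bullet's subject is also unclear: it may have been meant for one preceding item only, or for the admission items. Participants are healthy at entry, section 8.2.2 plans no safety laboratory tests, and SAP 18.1 restricts AE summaries to events that start at or after vaccination. On the holding rule, condition 1 alone cannot meet rule 2, because the rule needs relatedness. Its result is a pause for IDMC review, not termination.

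All of this stands, and it limits the size of the problem. It does not remove the conflict. Condition 2 does not depend on worsening, so it can apply to listed events that have not worsened, and it is the condition that matches rule 2. The unclear subject of the bullet is itself a reason to amend it.

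A reader might go further and infer that the SAE rate is inflated, or that the comparison between groups is biased. The documents support neither. No rate is given, so the most that can be said is that the rate can be inflated. Data collection is observer-blind and allocation is minimized on country and center, so differences in how sites read the text should fall about equally across groups. SAP section 18 plans no statistical comparison of safety data.

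It would also be too strong to say that nothing checks seriousness. The SAP describes no such step, but the expedited report form and the data-management documents are not among the papers available here.

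**Conclusion.** The concern holds as an internal contradiction with limited reach. As written, the last bullet of the not-an-AE list gives an SAE label without a seriousness outcome. The SAE section and the intensity section do not allow that, and the bullet does not say which events it covers.

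If it is followed literally, each affected child adds 0.5 percentage points to the SAE percentage of a 200-child group. One affected child with a related event, among the first 200, is enough to meet holding rule 2 on its wording. How often this would happen is unknown. It depends on p, on how sites read the bullet, and on any check of seriousness outside these documents. A reader might take the 63% figure as a sign that a pause is likely, but it rests on an assumed rate of 0.5%; at 0.01% the chance is 2%.

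The immunogenicity analyses and the sample size are not affected. The correction is worth making because the label feeds a named endpoint and a rule with a threshold of one, and because it costs little.

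**What to change.** - **Protocol Appendix 4.** The sponsor should reconcile the last bullet of the not-an-AE list with the box before it, the SAE section and the intensity section, and state which listed events the bullet covers. It should make clear that the SAE label carries one definition throughout, including in the endpoint and in Table 9. Which definition applies is for the sponsor to settle. This point proposes no change to the holding rules or their thresholds.
- **SAP 18.1.4.** State that the SAE tables count events that meet the reconciled definition. List separately any event that came by the expedited route without a seriousness outcome. If the first 200 children have already passed Day 43, this part still protects the endpoint.

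The cost is a one-sentence clarification to sites, a sentence in the SAP and one extra listing. Prompt notification of such events can be kept, so no safety information is lost.

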## Serious Adverse Events

If an event is not an AE per definition above, then it cannot be an SAE even if serious conditions are met (e.g., hospitalization for signs/symptoms of the disease under study).

An SAE is defined as any untoward medical occurrence that, at any dose:
a) Results in death
b) Is life-threatening
The term “life-threatening” in the definition of “serious” refers to an event in which the participant was at risk of death at the time of the event. It does not refer to an event that hypothetically might have caused death had it been more severe.
c) Requires inpatient hospitalization or prolongation of existing hospitalization
In general, hospitalization signifies that the participant has been admitted at the hospital or emergency ward for observation and/or treatment that would not have been appropriate in the physician’s office or in an out-patient setting. Complications that occur during hospitalization are also considered as AEs. If a complication prolongs hospitalization or fulfills any other serious criteria, the event will also be considered serious. When in doubt as to whether “hospitalization” occurred or was necessary, the AE should be considered serious.
d) Results in disability/incapacity
The term disability means a substantial disruption of a person’s ability to conduct normal life functions. This definition is not intended to include experiences of relatively minor medical significance such as uncomplicated headache, nausea, vomiting, diarrhea, influenza-like illness, and accidental trauma (e.g., sprained ankle) which may interfere or prevent everyday life functions but do not constitute a substantial disruption.
e) Other situations

 
Medical or scientific judgment should be exercised in deciding whether reporting is appropriate in other situations, such as important medical events that may not be immediately life-threatening or result in death or hospitalization but may jeopardize the participant or may require medical or surgical intervention to prevent one of the other outcomes listed in the above definition. These should also be considered serious. Examples of such events are invasive or malignant cancers, intensive treatment in an emergency department or at home for allergic bronchospasm, blood dyscrasias, or convulsions that do not result in hospitalization.
 

## Solicited Events

Solicited Events will include the following:
a) Solicited administration site events
The following administration site events will be solicited for toddlers 12 to 15 months of age at the time of the study intervention: 
 
Pain
 
Redness
 
Swelling
 

b) Solicited systemic events
The following systemic events will be solicited for toddlers 12 to 15 months of age at the time of the study intervention:

**Solicited Events will include the following:**

- Fever
- Varicella-like rash (including injection site varicella-like rash)
- General rash (not varicella-like)
- Drowsiness
- Loss of appetite
- Irritability

Note: participants' parent(s)/LAR(s) will be instructed to measure and record body temperature in the evening using the temperature measuring device provided by GSK. The recommended route of temperature measurement will be the axilla. Should additional temperature measurements be performed at other times of day, participants' parent(s)/LAR(s) will be instructed to record the highest temperature in the eDiary/personal electronic device app.

**Unsolicited Events****Definition of an Unsolicited Adverse Event:**

An unsolicited AE is an AE that was not included in a list of solicited events using an eDiary/personal electronic device app. Unsolicited events must have been spontaneously communicated by a participant's parent(s)/LAR(s) who have signed the informed consent. Unsolicited AEs include both serious and non-serious AEs.

Potential unsolicited AEs may be medically attended (i.e., symptoms or illnesses requiring a hospitalization, or an emergency room visit, or visit to/by a health care provider). The participant's parent(s)/LAR(s) will be instructed to contact the site as soon as possible to report medically attended event(s), as well as any events that, though not medically attended, are of participant/parental/LAR(s)' concern. Detailed information about reported unsolicited AEs will be collected by qualified study center personnel and documented in the participant's records.

Unsolicited AEs that are not medically attended or perceived as a concern by the participant's parent(s)/LAR(s) will be collected during an interview with the participant's parent(s)/LAR(s) and by review of available medical records at the next visit.

**COVID-19 Cases**

Diagnosis of COVID-19 should be made in accordance with the WHO case definition. Cases should be categorized as AEs (unsolicited or AEs leading to withdrawal) or SAEs, and routine procedures for recording, evaluation, follow-up, and reporting of AEs and SAEs should be followed in accordance with the time period set out in the protocol.

**Assessment of Intensity and Toxicity**

The intensity of the following solicited AEs will be assessed as described in [Table 13](#).

**Table 13      Intensity Scales for Solicited Symptoms in Toddlers (12 to 15 Months of Age)**

Toddler (12 to 15 months of age)		
Adverse Event	Intensity Grade	Parameter
Pain at injection site	0	None
	1	Mild: Minor reaction to touch
	2	Moderate: Cries/protests on touch
	3	Severe: Cries when limb is moved/spontaneously painful
Redness at injection site		Greatest surface diameter in mm
Swelling at injection site		Greatest surface diameter in mm
Fever*		Temperature in °C/°F
Varicella-like rash**		Number of lesions
General rash (not varicella-like)	0	None
	1	Mild: Rash which is easily tolerated by the child, causing minimal discomfort and not interfering with everyday activities
	2	Moderate: Rash which is sufficiently discomforting to interfere with normal everyday activities
	3	Severe: Rash which prevents normal, everyday activities (in a young child, such an AE would, for example, prevent attendance at school/day care and would cause the parent(s)/LAR(s) to seek medical advice)
Drowsiness	0	Behavior as usual
	1	Mild: Drowsiness easily tolerated
	2	Moderate: Drowsiness that interferes with normal activity
	3	Severe: Drowsiness that prevents normal activity
Loss of appetite	0	Appetite as usual
	1	Mild: Eating less than usual/no effect on normal activity
	2	Moderate: Eating less than usual/interferes with normal activity
	3	Severe: Not eating at all
Irritability	0	Behavior as usual
	1	Mild: Crying more than usual/no effect on normal activity
	2	Moderate: Crying more than usual/interferes with normal activity
	3	Severe: Crying that cannot be comforted/prevents normal activity

\*Fever is defined as temperature  $\geq 38.0^{\circ}\text{C}$  ( $100.4^{\circ}\text{F}$ ) by any route. The preferred location for measuring temperature will be the axilla.

\*\*A typical varicella-like rash manifests as a rash/lesions that may appear within 2 weeks (or sometimes later) after the varicella vaccination. Lesions may contain spots, bumps, blisters, or crusts. Refer to the Study Reference Manual for detailed varicella-like rash guidelines.

The maximum intensity of administration site redness/swelling/fever/varicella-like rash will be scored as follows:

	Redness/swelling	Varicella-like rash*	Fever†
0	None	None	$< 38.0^{\circ}\text{C}$ ( $100.4^{\circ}\text{F}$ )
1	$> 0 - \leq 5$ mm	1-25 lesions	$\geq 38.0^{\circ}\text{C}$ ( $100.4^{\circ}\text{F}$ ) - $\leq 39.0^{\circ}\text{C}$ ( $102.2^{\circ}\text{F}$ )
2	$> 5 - \leq 20$ mm	26-50 lesions	$> 39.0^{\circ}\text{C}$ ( $102.2^{\circ}\text{F}$ ) - $\leq 39.5^{\circ}\text{C}$ ( $103.1^{\circ}\text{F}$ )
3	$> 20$ mm	$\geq 51$ lesions	$> 39.5^{\circ}\text{C}$ ( $103.1^{\circ}\text{F}$ )

\*Including injection site varicella-like rash

†Temperature will be analyzed in  $0.5^{\circ}\text{C}$  increments from  $\geq 38.0^{\circ}\text{C}$  ( $\geq 100.4^{\circ}\text{F}$ ).

The investigator will assess the maximum intensity that occurred over the duration of the event for all unsolicited AEs (including SAEs) recorded during the study. The assessment will be based on the investigator's clinical judgment.

The intensity should be assigned to 1 of the following categories:

- 1 (mild) = An AE that is easily tolerated by the participant, causing minimal discomfort and not interfering with everyday activities.
- 2 (moderate) = An AE that is sufficiently discomforting to interfere with normal everyday activities.
- 3 (severe) = An AE that prevents normal everyday activities. Such an AE would, for example, prevent attendance at a childcare facility and would cause the parent(s)/LAR(s) to seek medical advice.

An AE that is assessed as Grade 3 (severe) should not be confused with an SAE.

Grade 3 is a category used for rating the intensity of an event; and both AEs and SAEs can be assessed as Grade 3. An event is defined as "serious" when it meets one of the pre-defined outcomes as described above.

